#### **4.4.2. Clinical Studies of CTP-543**

Two clinical studies with CTP-543 in healthy volunteers have been completed. Study CP543.1001 was a pharmacokinetic/pharmacodynamic study consisting of a first-in-human single ascending dose study and a sequential multiple ascending dose study. The objective of the study was to assess safety, tolerability, pharmacokinetics, and pharmacodynamics of CTP-543 in healthy volunteers. A total of 82 subjects were planned for the study; 32 subjects in 4 cohorts randomized at a ratio of 3:1 CTP-543 to placebo for the single ascending dose part (Part A), and thereafter, 50 subjects in 5 cohorts randomized at a ratio of 4:1 CTP-543 to placebo for the multiple ascending dose part (Part B). The doses studied in the single ascending dose study were 8 mg, 16 mg, 32 mg, and 48 mg. The doses studied in the multiple ascending dose study were 8 mg once daily, 8 mg twice daily, 24 mg once daily, 32 mg once daily, and 16 mg twice daily, dosed for 7 consecutive days.

The second clinical study CP543.1002, also performed in healthy volunteers was a single dose cross-over study to assess safety and tolerability and to compare the metabolite and pharmacokinetic profiles of CTP-543 versus ruxolitinib. A total of 12 subjects were enrolled in the study; 2 groups of 6 subjects each were dosed with either 15 mg of ruxolitinib (1 x 15 mg tablet) or 16 mg of CTP-543 (2 x 8 mg tablets) in period 1 who then crossed over to the alternate treatment for period 2. A washout period of 3 days occurred between treatments.

To date, CTP-543 has been generally well tolerated. No deaths or serious adverse events have occurred following dosing with CTP-543.

## **5. ETHICS**

The procedures set out in this study protocol, pertaining to the conduct, evaluation and documentation of this study, are designed to ensure that the Sponsor and the Investigator abide by Good Clinical Practice (GCP), including but not limited to Title 21 Code of Federal Regulations (CFR) Parts 50, 56, and 312, and the International Conference on Harmonisation (ICH) guidelines and directives. Compliance with these regulations also constitutes compliance with the ethical principles described in the current revision of the Declaration of Helsinki and applicable local regulatory requirements and law.

The Investigator is responsible for protecting the rights, safety, and welfare of patients under his/her care, and for the control of the medications under investigation. All ethical, regulatory, and legal requirements must be met before the first patient is enrolled in the study.

### **5.1. Institutional Review Board (IRB)**

The Institutional Review Board (IRB) will meet all FDA requirements governing IRBs according to CFR, Title 21, Part 56. The Investigator (or designee) must submit this study protocol and any amendments, the Sponsor's approved informed consent form(s) (ICF), patient information sheets, patient recruitment materials, and other appropriate documents to the IRB for review and approval. Following review of the submitted materials a copy of the written and dated approval/favorable opinion will be forwarded to the Sponsor (or designee).

Any advertisements used to recruit patients for the study will be reviewed by the Sponsor and the IRB prior to use.

### **5.2. Written Informed Consent**

Prior to performing any study-related activities under this protocol, including screening tests and assessments, written informed consent with the approved ICF must be obtained from the patient.

The ICF, as specified by the clinical site's IRB, must follow the Protection of Human Subjects regulations listed in the Code of Federal Regulations, Title 21, Part 50. The background of the proposed study, the procedures, the benefits and risks of the study, and that study participation is voluntary must be explained to the patient. The patient must be given sufficient time to consider whether to participate in the study.

A copy of the ICF, signed and dated by the patient, must be given to the patient. Confirmation of a patient's informed consent must also be documented in the patient's source documentation prior to any testing under this protocol, including screening tests and assessments. The original signed consent form will be retained with the study records.

All ICFs used in this study must be approved by the appropriate IRB and by the Sponsor. The ICF must not be altered without the prior agreement of the relevant IRB and the Sponsor.

## **6. STUDY OBJECTIVES**

The overall objectives of the study are to assess the safety and efficacy of a 24-week regimen of administration of CTP-543 in adult patients with chronic, moderate to severe alopecia areata.

### **6.1. Primary Objectives**

The primary objectives are:

- To assess the efficacy of CTP-543 on hair loss as measured by the Severity of Alopecia Tool (SALT);
- To assess the safety of administration of CTP-543 in adult patients with chronic, moderate to severe alopecia areata.

### **6.2. Exploratory Objectives**

The exploratory objectives are:

- To assess the change in patient alopecia areata severity as measured by the clinician Visual Analog Scale;
- To assess the change in Clinical Global Impression of Improvement (CGI-I) from baseline;
- To assess the change in alopecia areata severity as measured by the patient Visual Analog Scale from baseline;
- To assess the change in Patient Global Impression of Improvement (PGI-I) from baseline;
- To assess the change in patient reported outcomes as measured by the Alopecia Areata Symptom Impact Scale (AASIS) and exploratory questions from baseline;
- To evaluate the plasma concentrations of CTP-543 in adult patients with chronic, moderate to severe alopecia areata.

## 7. OVERALL STUDY DESIGN

### 7.1. Study Design

This is a double-blind, randomized, placebo-controlled, multicenter study to evaluate the safety and efficacy of CTP-543 in adult patients with chronic, moderate to severe alopecia areata. Patients will require a definitive diagnosis of alopecia areata by the Investigator based on clinical evaluation involving physical examination and medical history. The patient's alopecia areata will be classified by the Investigator into one of three categories defined for this study:

- 1) Alopecia areata: patchy type hair loss,
- 2) Alopecia totalis or universalis: complete hair loss on the scalp with or without body hair loss,
- 3) Alopecia ophiasis: band-like hair loss limited to the periphery of the scalp along the back of the hair line in the occipital region and possibly extending over each ear in temporal regions.

[figure not shown]
Patients will be between 18 and 65 years of age and experiencing a current episode of alopecia areata lasting at least 6 months and not exceeding 10 years. Total disease duration may exceed the duration of the current episode. Patients will require at least 50% hair loss as measured by the SALT assessment at Screening and Baseline, and should not be treated concurrently for alopecia areata or with other treatments that might affect hair regrowth. Approximately 50% of alopecia areata patients with alopecia totalis or universalis, and approximately 10% with only alopecia ophiasis, will be enrolled.

The study consists of up to 3 cohorts initiated sequentially in ascending dose order. An independent data monitoring committee (DMC) will determine if there are adequate safety data to support each subsequent dose cohort. Patients will not dose escalate within a cohort and may only participate in one cohort.

The Screening Period will last up to 28 days prior to initiation of study drug. The Treatment Period is the initial 24-week, double-blind, placebo-controlled period to define primary efficacy and safety for the study. The Post-Treatment Safety Follow-up Period is the final 4 weeks of each cohort to assess safety following treatment completion. Subjects enrolled in Cohort 3 (12 mg BID) will have the option to continue receiving treatment in an Open-label Extension study following the treatment period. If subjects do not wish to continue into the Open-label Extension study, they will complete treatment at Week 24 and return in 4 weeks for the Post-Treatment Safety Follow-up to assess safety following treatment completion.

The DMC will perform regular safety assessments for each cohort based on review of collective safety data. After the last patient in a cohort has completed the Week 12 Visit, the DMC will convene to review accumulated safety data to assess if initiation of the subsequent cohort is supported, as applicable. The DMC may advise treatment arm cessation due to intolerability at any time.

**Figure 1: Study Design**

Patients will provide appropriately obtained informed consent prior to completing any screening procedures. Patients meeting initial screening criteria will be eligible to continue to the cohort Day 1 visit for review of eligibility and baseline assessments, including SALT assessment, physical examination, clinical laboratory assessments, vital signs, and electrocardiogram. The first 2 cohorts will be randomized in a 2:1 ratio (active:placebo) and the third cohort will be randomized in a 5:1 ratio (active:placebo) in order to provide a similar number of patients across the CTP-543 and pooled placebo arms. Randomization will be stratified by classification of alopecia areata subtype into one of the following three categories: 1) alopecia areata, 2) alopecia totalis or alopecia universalis, or 3) alopecia ophiasis.

The double-blind, placebo-controlled Treatment Period for each cohort will last 24 weeks. Assessment of treatment response with SALT for efficacy will occur at 4, 8, 12, 16, 20 and 24 weeks. All SALT assessments will be performed with a live physical examination of the patient by qualified, trained site personnel. Photographs of the scalp will be used to provide a visual record at the time of SALT assessment, and photographs of the hands and/or eyes will be taken to document nail or eyelash/eyebrow involvement in those patients for whom it applies. The

efficacy analysis will be conducted when all patients in the highest dose cohort have completed Week 24 of dosing.

For Cohorts 1 and 2, patients will stop taking study medication upon completion of treatment at Week 24, and enter a 4 week Post-Treatment Safety Follow-Up Period. Patients will be assessed for safety through Week 28. For Cohort 3 (12 mg BID), patients will be eligible to either complete treatment at Week 24 and exit the study at Week 28 following the Safety Follow-up visit, or roll-over into a Long-term Extension study at Week 24.

Patients enrolled into each cohort will take the first dose of study drug in the clinic on Day 1 and will be instructed to take study drug every 12 hours with or without food, for the duration of the Treatment Period. Patients should dose study drug in the clinic on all Study Visit Days after clinical laboratory blood draws are completed. Blood samples for pharmacokinetic and pharmacodynamic assessment will be taken periodically. Scheduled assessment of patient and clinician perception of disease severity and improvement will also occur. Patient safety will be monitored throughout the study by the Investigators, and supported by regular review by the Medical Monitor, and DMC. Hematology parameters will be monitored closely for the duration of the study. For each cohort, hematology will be conducted every 2 weeks during the first 8 weeks of the Treatment Period, followed by an assessment every 4 weeks thereafter through completion of the study. Lipid levels will be assessed every 12 weeks throughout the Treatment Period and at the Post-Treatment Safety Follow-Up Visit, if applicable. Significant cytopenias or other hematologic abnormalities will be managed by severity through dose interruption or discontinuation, and signs and symptoms of infection will be closely monitored and treated promptly. Patients who experience intolerable symptoms during treatment may discontinue the study at the discretion of the Investigator. Patients may withdraw consent at any time.

## **7.2. Number of Patients and Sites**

Approximately 150 patients are planned to be enrolled in the study at up to 14 sites. The first 2 cohorts will be randomized in a 2:1 ratio and the third cohort will be randomized in a 5:1 ratio in order to provide a similar number of patients across the CTP-543 and pooled placebo arms.

## **7.3. Method of Treatment Assignment and Blinding**

Randomization will be stratified by classification of alopecia areata subtype into one of the following three categories: 1) alopecia areata, 2) alopecia totalis or alopecia universalis, and 3) alopecia ophiasis. Approximately 50% of alopecia areata subjects with alopecia totalis or universalis, and approximately 10% with only alopecia ophiasis, will be enrolled. The randomization schedule will be generated prior to study start.

All study participants will be blinded to study drug assignment for the duration of the study. Tablets and packaging of CTP-543 and placebo will be identical in appearance.

## **7.4. Rationale for Study Design**

Double-blind, randomized, placebo-controlled studies are considered optimal for obtaining unbiased estimates of the efficacy and safety of investigational products. The 24-week duration of the Treatment Period is anticipated to allow sufficient time for initiation of hair growth with CTP-543. Assessment of treatment through 24 weeks will provide an initial assessment of the safety profile associated with CTP-543.

## **8. SELECTION AND WITHDRAWAL OF PATIENTS**

Patients eligible for enrollment in the study must meet all of the following inclusion criteria and none of the exclusion criteria.

### **8.1. Patient Inclusion Criteria**

1. Written informed consent, and authorization for release and use of protected health information.
2. Between 18 and 65 years of age, inclusive, at the time of informed consent.
3. Definitive diagnosis of alopecia areata with a current episode of at least 6 months and not exceeding 10 years at the time of Screening. Total disease duration greater than 10 years is permitted.
4. At least 50% scalp hair loss, as defined by a SALT score  $\geq 50$ , at Screening and Baseline.
5. If of reproductive age, willing and able to use a medically highly effective form of birth control during the study and for 30 days following last dose of study medication.  
Examples of medically highly effective forms of birth control are:
  - a. Surgical sterility (via vasectomy, hysterectomy or bilateral ligation) or post-menopausal females
  - b. Sexual partner is sterile, or of the same sex
  - c. Implants of levonorgestrel in females
  - d. Oral contraceptive (combined or progesterone only) in females
  - e. Double-barrier method (any combination of physical and chemical methods)
  - f. Intrauterine device in females, or other method with published data showing that the lowest expected failure rate is less than 1% per year
6. Willing to comply with the study visits and requirements of the study protocol.

### **8.2. Patient Exclusion Criteria**

1. History or presence of hair transplants.
2. Treatment with other medications or agents within 1 month of Screening or during the study that may affect hair regrowth or immune response, including, but not limited to: corticosteroids administered orally, by injection, or applied to areas of skin affected by alopecia; platelet-rich plasma injections; topical application to affected areas of anthralin, squaric acid, diphenylcyclopropenone, or minoxidil.
3. Treatment with systemic immunosuppressive medications including but not limited to methotrexate, cyclosporine, and azathioprine; chloroquine derivatives; JAK inhibitors (ruxolitinib, tofacitinib, etc) or etanercept within 3 months of Screening or during the study; or biologics (adalimumab, atlizumab, canakinumab, certolizumab, fontolizumab, golimumab, infliximab, mepolizumab, rituximab, secukinumab, tocilizumab, ustekinumab) within 6 months of Screening or during the study.
4. Active scalp inflammation, psoriasis, or seborrheic dermatitis requiring topical treatment to the scalp, significant trauma to the scalp, or untreated actinic keratosis anywhere on the body at Screening and/or Baseline.

5. Known history of moderate to severe androgenic alopecia or female pattern hair loss prior to alopecia areata.
6. Unwilling to maintain a consistent hair style, including shampoo and hair products (including hair dye, process, and timing to hair appointments), and to refrain from weaves or extensions throughout the course of the study, or shaving of scalp hair for at least 2 weeks prior to a SALT assessment.
7. Use of adhesive wigs, other than banded perimeter wigs, during the study.
8. History of a lymphoproliferative disease or malignancy, other than non-melanoma skin cancer or cervical carcinoma. Patients with 3 or more basal or squamous cell carcinomas diagnosed in the past 2 years are excluded.
9. Atypical nevi or cutaneous lesions that are suspicious for malignancy.
10. History of solid organ or hematological transplantation.
11. Fever or infection within 2 weeks prior to first dose of study drug.
12. Abnormal levels of thyroid stimulating hormone at Screening, defined as  $<0.9 \times$  the lower limit of normal (LLN) and  $>1.2 \times$  the upper limit of normal (ULN) and, if taking thyroid medication, an inability to maintain levels within the normal range for 6 months prior to Screening or during the study.
13. Screening labs outside the normal range for parameters associated with potential risk for treatment under investigation. This will include but is not limited to:
  - a. Platelets  $\leq 120 \times 10^9/L$
  - b. Absolute neutrophil count  $\leq 1.5 \times 10^9/L$
  - c. Hemoglobin levels  $\leq 11$  g/dL for females, or hemoglobin levels  $\leq 12.5$  g/dL for males
14. Screening blood glucose levels of hemoglobin A1c  $\geq 6.5\%$  (48 mmol/mol).
15. Abnormal liver function at Screening, defined as  $\geq 1.5 \times$  ULN of serum alanine transaminase, serum aspartate transaminase, serum alkaline phosphatase, or total bilirubin (unless isolated Gilbert's syndrome).
16. Abnormal renal function (estimated glomerular filtration rate  $<60$  mL/min/1.73 m^2 using the MDRD equation) at Screening.
17. Any active infection at Screening, active or previous Hepatitis B or C infection, or known human immunodeficiency virus infection.
18. Vaccination with herpes zoster vaccine or any live virus vaccine within 6 weeks before Screening or during the study.
19. Positive purified protein derivative test for non-bacillus Calmette-Guérin-vaccinated patients, positive QuantiFERON®-TB Gold test, or history of incompletely treated or untreated tuberculosis.
20. History of prolonged QT syndrome or a Screening QTc interval with Fridericia's correction (QTcF)  $> 450$  msec for males or QTcF  $> 470$  msec for females.
21. History of alcohol, medication, or illicit drug abuse within 1 year before the first dose of study drug.

22. Females who are nursing, pregnant, or planning to become pregnant while in the study, and for 30 days after last dose of study medication.
23. Participation in another investigational study within the greater of 4 weeks or 5 half-lives of an investigational medication prior to screening or during the study.
24. Use of strong CYP3A4 inhibitors (such as, but not limited to clarithromycin, conivaptan, grapefruit juice, indinavir, itraconazole, ketoconazole, lopinavir/ritonavir, mibefradil, nefazodone, nelfinavir, posaconazole, saquinavir, telaprevir, telithromycin, voriconazole, or fluconazole) dosed for systemic exposure.
25. Use of strong CYP3A4 inducers (such as, but not limited to barbiturates, carbamazepine, efavirenz, glucocorticoids, modafinil, nevirapine, oxcarbazepine, phenobarbital, phenytoin, pioglitazone, rifabutin, rifampin, St. John's Wort, or troglitazone) dosed for systemic exposure.
26. Donation of blood within a month of first dose of study drug or at any point throughout the study and for 30 days after last dose of study medication.
27. Clinically significant medical condition, psychiatric disease, or social conditions, as determined by the Investigator, that may unfavorably alter the risk-benefit of study participation, adversely affect study compliance, or confound interpretation of study results.

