***Exclusion Criteria:***

1. History or presence of hair transplants.
2. Treatment with other medications or agents within 1 month of Screening or during the study that may affect hair regrowth or immune response, including but not limited to: corticosteroids administered orally, by injection, or applied to areas of skin affected by alopecia; platelet-rich plasma injections; topical application to affected areas of anthralin, squaric acid, diphenylcyclopropenone, or minoxidil.
3. Treatment with systemic immunosuppressive medications including but not limited to methotrexate, cyclosporine, and azathioprine; chloroquine derivatives; Janus kinase inhibitors (ruxolitinib, tofacitinib, etc) or etanercept within 3 months of Screening or during the study; or biologics (adalimumab, atlizumab, canakinumab, certolizumab, fontolizumab, golimumab, infliximab, mepolizumab, rituximab, secukinumab, tocilizumab, ustekinumab) within 6 months of Screening or during the study.
4. Active scalp inflammation, psoriasis, or seborrheic dermatitis requiring topical treatment to the scalp, significant trauma to the scalp, or untreated actinic keratosis anywhere on the body at Screening and/or Baseline.
5. Known history of moderate to severe androgenic alopecia or female pattern hair loss prior to alopecia areata.
6. Unwilling to maintain a consistent hair style, including shampoo and hair products (including hair dye, process, and timing to hair appointments), and to refrain from weaves or extensions throughout the course of the study, or shaving of scalp hair for 2 weeks preceding a SALT assessment.
7. Use of adhesive wigs, other than banded perimeter wigs, during the study.
8. History of a lymphoproliferative disease or malignancy, other than non-melanoma skin cancer or cervical carcinoma. Patients with 3 or more basal or squamous cell carcinomas diagnosed in the past 2 years are excluded.
9. Atypical nevi or cutaneous lesions that are suspicious for malignancy.
10. History of solid organ or hematological transplantation.
11. Fever or infection within 2 weeks prior to first dose of study drug.

12. Abnormal levels of thyroid stimulating hormone at Screening, defined as  $<0.9 \times$  the lower limit of normal (LLN) and  $>1.2 \times$  the upper limit of normal (ULN) and, if taking thyroid medication, an inability to maintain levels within the normal range for 6 months prior to Screening or during the study.

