
AASIS = Alopecia Areata Symptom Impact Scale; HBV= hepatitis B virus; HCV = hepatitis C virus
 
 All subsequent visits and week increments should be based on the date of Visit 2. All visit windows are <math>\pm 3</math> days.
 
 Serum pregnancy test only for females of childbearing potential.
 
 Includes hematology and serum chemistry.
 
 Will include thyroid stimulating hormone and hemoglobin A1c at Screening only.
 
 Includes total cholesterol, low-density lipoprotein, high-density lipoprotein, and triglycerides.
 
 Collected at Day 1 and Week 4 (pre-dose, and post-dose at end of visit), and Weeks 2 (pre-dose with clinical labs), and Weeks 8, 24 (post-dose at end of visit).
	
 Collected at Day 1 and Week 2 (pre-dose with clinical labs), and Weeks 4, 8, 24 (post-dose at end of visit). Collected pre-dose.
 
 Should be performed by the same rater for the patient for the duration of the study.
 
 Collection is ongoing.
 
 Also serves as the Early Termination Visit for patient withdrawal.
 
 Randomization/Day 1 may occur any time after Screening laboratory results are available and reviewed by the Investigator.
 
 The Safety Follow-Up Visit is intended for those patients in Cohort 1 and Cohort 2, and those patients in Cohort 3 who do not roll over into the Open-label Extension.

---	--

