### **9.5. Concomitant Medications and Procedures**

All medications, including over-the-counter therapies (e.g., vitamins, herbal, and nutritional supplements), taken at the time of the Screening Visit through the Follow-Up Visit will be recorded in the patient's source documentation and documented in the eCRF.

If taking thyroid medication, the patient must maintain thyroid stimulation hormone levels within the normal range for 6 months prior to Screening and throughout the study.

Any concomitant medication deemed necessary for the wellbeing of the subject may be given at the discretion of the Investigator. Use of medications that are prohibited per protocol will require patient withdrawal from the study.

The following treatments are not permitted during the study:

- Medications that may affect hair regrowth or immune response (such as: corticosteroids administered orally, by injection, or applied to areas of skin affected by alopecia; platelet-rich injections; topical application to affected areas of anthralin, squaric acid, diphenylcyclopropenone, or minoxidil;
- Treatment with systemic immunosuppressive medications including but not limited to methotrexate, cyclosporine, and azathioprine; chloroquine derivatives; Janus kinase inhibitors (ruxolitinib, tofacitinib, etc), etanercept; or biologics (adalimumab, atlizumab, canakinumab, certolizumab, fontolizumab, golimumab, infliximab, mepolizumab, rituximab, secukinumab, tocilizumab, ustekinumab);
- Use of strong CYP3A4 inhibitors (such as, but not limited to clarithromycin, conivaptan, grapefruit juice, indinavir, itraconazole, ketoconazole, lopinavir/ritonavir, mibefradil, nefazodone, nelfinavir, posaconazole, saquinavir, telaprevir, telithromycin, voriconazole, or fluconazole) dosed for systemic exposure;
- Use of strong CYP3A4 inducers (such as, but not limited to barbiturates, carbamazepine, efavirenz, glucocorticoids, modafinil, nevirapine, oxcarbazepine, phenobarbital, phenytoin, pioglitazone, rifabutin, rifampin, St. John's Wort, or troglitazone) dosed for systemic exposure.

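### Exclusion 12 joins its low and high TSH limits with *and*, so no value can meet them; its medication clause is ambiguous and its on-study requirement has no scheduled test

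*Protocol*

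**What the plan says.** Criterion 12 has the same wording in the Synopsis exclusion list and in Protocol Section 8.2. It opens with "Abnormal levels of thyroid stimulating hormone at Screening", continues "defined as $<0.9 \times$ the lower limit of normal (LLN) and $>1.2 \times$ the upper limit of normal (ULN"), and then adds "and, if taking thyroid medication, an inability to maintain levels within the normal range for 6 months prior to Screening or during the study".

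Section 8 sets how the list operates: eligible patients "must meet all of the following inclusion criteria and none of the exclusion criteria".

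Section 9.5 has a separate thyroid rule for patients on thyroid medication: "the patient must maintain thyroid stimulation hormone levels within the normal range for 6 months prior to Screening and throughout the study".

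On timing, footnote 4 to Table 1 says of laboratory testing: "Will include thyroid stimulating hormone and hemoglobin A1c at Screening only". SAP Section 17.2 repeats that footnote. The SAP does not restate criterion 12; its Section 2.3 refers the reader to Protocol Sections 8.1 and 8.2.

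**The concern.** An exclusion criterion works only if some patient can meet it. Criterion 12 has three weaknesses.

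- **First conjunction.** A low limit and a high limit on the same measurement are joined by *and*.
- **Second conjunction.** The medication clause is attached by another *and*. The text does not say whether it narrows the TSH limits or is a ground of its own.
- **On-study requirement.** Patients on thyroid medication must stay in the normal range during the study, but no TSH test is scheduled after Screening.

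At stake are consistent enrolment across sites and the classification of eligibility deviations. Under SAP Sections 4.4 and 5.2, major deviations remove patients from the Per Protocol population. Whether a patient enrolled with TSH outside a limit is an eligibility deviation under criterion 12 depends on how the criterion is read. Testing is based on the Efficacy population (SAP Section 8.4), so there the wording matters only through who was enrolled.

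**Working it through.** The plan gives no figure to reproduce here. The check is one of logic.

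**Step 1: can both TSH limits hold?** Let A be TSH < 0.9 × LLN and B be TSH > 1.2 × ULN (both from criterion 12). A and B together need

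1.2 × ULN < TSH < 0.9 × LLN,

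which requires ULN/LLN < 0.9/1.2 = 0.75. Since ULN exceeds LLN, the ratio is above 1 and no value qualifies. This holds for any reference range, so it does not matter that the documents give none for TSH. A numerical check with 1,000,000 arbitrary TSH values and reference intervals agreed: 0 met A and B, while 456,016 + 154,763 = 610,779 met A or B. Those counts reflect assumed distributions and do not estimate how many patients would be excluded.

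**Step 2: what does the second *and* do?** Let C be the medication clause. Where C is a further condition, a patient not on medication is taken to satisfy it. Where C stands alone, only a patient on medication who cannot maintain normal levels meets it. The entries show whether criterion 12 excludes the patient.

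| Patient | A and B and C | (A and B), or C alone | (A or B) and C | A or B or C |
|---|---|---|---|---|
| Not on medication, TSH outside one limit | No | No | Yes | Yes |
| On medication, levels not maintained, TSH outside one limit | No | Yes | Yes | Yes |
| On medication, levels not maintained, TSH not beyond either limit | No | Yes | No | Yes |
| On medication, levels maintained, TSH outside one limit | No | No | No | Yes |

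The first two readings keep the printed *and* between the limits. The last two replace it with *or*.

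- With the printed *and*, the unmedicated patient outside a limit is not excluded on either reading of C.
- Changing only the first *and* does not settle the criterion. The third and fourth rows still differ between the last two columns.
- The third row is a realistic case. A patient on medication with Screening TSH between 1.0 and 1.2 × ULN is outside the normal range but inside the exclusion limit.

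**Step 3: compare with the rest of the protocol.** Section 9.5 makes the medication requirement independent of the 0.9 and 1.2 multiples, which fits C standing alone. Criteria 13c, 15 and 20 join alternative limits or parameters with *or*, and criterion 4 uses *and/or*, so criterion 12 departs from the protocol's own usage.

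**Step 4: on-study testing.** Criterion 12 and Section 9.5 both extend the medicated patient's requirement into the study. Footnote 4 places TSH at Screening only. No scheduled test therefore checks the requirement.

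**The case against.** The strongest reply is that nobody would read the criterion as Boolean logic. It speaks of abnormal levels in the plural and lists a low range and a high range, and two limits serve no purpose unless either one excludes. That is persuasive about how sites probably applied the first *and*. It does not make the text correct, and it does not resolve the second *and*.

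There are also backstops. Criterion 13 covers "Screening labs outside the normal range for parameters associated with potential risk for treatment under investigation" and is open-ended. Criterion 27 lets the Investigator exclude a clinically significant condition. Section 9.5 covers patients on thyroid medication. These stand as partial protection, but neither 13 nor 27 names TSH, and 27 depends on judgment.

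A reader might infer three stronger things that the documents do not support:

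- **That criterion 12 excludes nobody.** This holds only if the medication clause is also a joint condition. If it stands alone, it excludes some patients on thyroid medication.
- **That there is no basis for recording a deviation.** Section 9.5 gives one for patients on thyroid medication, and SAP Section 5.2 lets the sponsor class as major any recorded deviation that could confound interpretation.
- **That the on-study requirement cannot be checked.** Section 10.13 allows Unscheduled Visits for safety monitoring, and Section 10.11 has additional relevant laboratory results reported to the sponsor. What is missing is a scheduled test.

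Nor does anything in the documents show that sites actually applied different readings. That remains a possibility only.

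**Conclusion.** The point holds as a drafting defect in operative eligibility text, with three parts: TSH limits that no value can meet as written, a medication clause whose role is unclear and which fits Section 9.5 only if it stands alone, and an on-study requirement with no scheduled test.

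The impossibility of meeting both limits rests only on ULN exceeding LLN. The practical effect is probably modest, because sites are likely to have treated either limit as excluding. The share of screened patients with TSH outside the limits, or on thyroid medication, is not in the documents, so no size can be given. No endpoint definition, sample size, power or significance level depends on this point. Whether the limits themselves are suitable is not judged here.

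**What to change.** Reword both conjunctions in criterion 12, in the Synopsis and in Section 8.2, so that the intended logic is explicit. If each TSH limit alone is meant to exclude, join them with *or*. State whether the medication clause is a separate ground or a further condition. Reconcile the result with Section 9.5, and reconcile the on-study requirement there and in criterion 12 with footnote 4 (repeated in SAP Section 17.2). No threshold needs to change.

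The cost is small: two conjunctions in two places plus the cross-references, at the next amendment.

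Timing limits what an amendment can do. Amendment 5 is dated 21 January 2019, and the Synopsis estimates that the last patient completes in July 2019. Counting 24 weeks (168 days) back from 31 July 2019 gives 13 February 2019 as about the latest start of treatment on that estimate. If enrolment has closed, the useful step is a short file note, written before the blinded review classifies deviations, that records which reading was applied and treats all patients alike for the Per Protocol population.
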